10.3.2 Other Efficacy Endpoints

In general, summaries are provided in frequency and percentage for both of assessments by investigators and subjects, and by subgroups at V12. No statistical testing will be performed for other efficacy endpoints.

10.3.2.1 Global Aesthetic Improvement Scale (GAIS)

There are two assessment categories in GAIS at V12; Subject rating and Investigator rating. Descriptive statistics in frequency and percentage of scales at end of the study, in the 5-point scale from -2 to +2 are provided for both of assessments by investigators and subjects, and by subgroups as well.

10.3.2.2 Periorbital Aesthetic Appearance Questionnaire (PAAQ)

Descriptive summaries are provided in frequency and percentage for nine (9) questions by treatment and subgroups at baseline and end of the study, with five categories of answers for each question. Change in subject's satisfaction with appearance of periorbital area as measured by the periorbital aesthetic appearance questionnaire (PAAQ). Transformed PAAQ scores are summarized in the same manner of the primary endpoint.

[REDACTED]

[REDACTED]

[REDACTED]

[REDACTED]

[REDACTED]

[REDACTED]

11 SAFETY ANALYSES

The safety analysis will be performed using the Full Analysis Population. The safety parameters will include adverse events (AEs). The last nonmissing safety assessment before the first dose of study treatment will be used as the baseline for all analyses of that safety parameter.

Categorical variables will be summarized by number and percentage of patients. No statistical test will be performed.

11.1 Adverse Events

All Adverse events (AEs) will be classified by Primary System Organ Class (SOC) and Preferred Term (PT) according to the Medical Dictionary for Regulatory Activities (MedDRA) Version 21.0 or newer.

TEAE is defined as an AE that was not present prior to treatment with investigational products but appeared following treatment or was present at treatment initiation but worsened after treatment or become SAE.

An SAE is defined as any AE that either led to death; resulted in a life-threatening illness or injury; resulted in a permanent impairment of a body structure or a body function; required in-patient hospitalization or prolongation of existing hospitalization; resulted in medical or surgical intervention to prevent permanent impairment to body structure or a body function; led to fetal distress, fetal death or a congenital abnormality or birth defect.

AE summary tables will be presented for TEAEs only and will include the following:

- All TEAEs
- TEAEs related to study drug
- TEAEs leading to study discontinuation
- Serious/Severe TEAEs
- Serious/Severe TEAEs related to study drugs
- TEAEs leading to death.

All TEAEs will be summarized by SOC, PT and treatment group using frequency counts and percentages (i.e., number and percentage of subjects with an event). In addition, an overall summary for the categories above will be prepared by treatment group and overall.

All TEAEs will be summarized by SOC, PT, maximum severity, and treatment group using frequency counts and percentages (i.e., number and percentage of subjects with an event)

An AE will be considered as related if the event is Possibly, Probably or Definitely related. If the relationship to study drug is missing, the AE will be treated as related. For AE with severity missing, the missing severity will be imputed as severe.

For the incidence at the subject level by SOC and PT, if a subject experiences more than one event within the same SOC and PT, only one occurrence will be included in the incidence. For the incidence at the subject level by SOC, PT, and severity, if a subject experiences more than one event within the same SOC and PT, only the most severe occurrence will be included in the incidence.

For the incidence at the subject level by SOC, PT, and relationship to investigational product, if a subject experiences more than one event within the same SOC and PT, only the most related occurrence will be included in the incidence.

For the summary of number of events, if a subject experiences more than one event within the same SOC and PT, all events will be counted.

All AEs will be listed, and additional listings will be presented for AEs leading to discontinuation, serious AEs and AEs resulted in deaths.

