 28. Mid-face volume deficit due to congenital defect, trauma, abnormalities in adipose tissue related to immune-mediated diseases such as generalized lipodystrophy (eg, juvenile dermatomyositis), partial lipodystrophy (eg, Barraquer-Simons syndrome), inherited disease, or human immunodeficiency virus-related disease
 29. Undergone oral surgery or other dental procedures (eg, tooth extraction, orthodontia, or implantation) within 30 days prior to enrollment or planning to undergo any of these procedures during the study
 30. Subjects with neuromuscular disorders including generalized muscle weakness, diplopia, ptosis, dysphonia, dysarthria, severe dysphagia, and respiratory compromise
 31. Subjects with a history of allergies or hypersensitivity to HA or lidocaine

Products, Dose, and Mode of Administration:

BELKYRA

Inject 0.2 mL in each site, 1 cm apart, up to 50 injections into the subcutaneous fat. The planned treatment area should be outlined with a surgical pen and a 1 cm injection grid applied to mark the injection sites. The maximum dose should not exceed 100 mg (10 mL) in a single treatment. The number of treatment sessions needed to achieve a satisfactory response depends on the individual patient. Up to 6 treatments spaced at intervals of no less than 1 month apart, are recommended based on the clinical trial efficacy and safety data. Patients should receive the minimum number of injections over a minimum number of treatment sessions to achieve a satisfactory result. More frequent dosing with BELKYRA has not been clinically evaluated for safety and effectiveness and is not recommended. The investigator will determine the number of treatment sessions based on his/her clinical experience and the subject's aesthetic goals.

SkinMedica Products

During Visit 7 to Visit 12, all subjects will receive a combination of the following SkinMedica products, to be applied daily for approximately 4 months, as per the investigator's discretion:

- Facial Cleanser
- TNS Essential Serum[®]
- Rejuvenative Moisturizer
- Optional: Total Defence + Repair Broad Spectrum Sunscreen SPF34 may be used at the subjects' discretion

BOTOX Cosmetic

Subjects will receive at least one of the following BOTOX Cosmetic dosing regimens:

- 20 U total to GLs area consisting of 5 injection sites (2 in each corrugator and one in the procerus), and/or
- CFLs: 2-6 U should be injected bilaterally at each of 1-3 injection sites and/or

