10.2 Medical Device

An AE from a medical device is defined as any undesirable physical, psychological or behavioral effect experienced by a subject during his/her participation in a study, in conjunction with the use of the device, whether or not it is considered related to the procedure or the product. Adverse events may include, but are not limited to, subjective or objective symptoms spontaneously offered by the subject, solicited via subject interviews, uncovered by review of concomitant medications, therapies, and treatments, and/or observed by the investigator. The investigator will record the description (sign, symptom and diagnosis), location, onset, resolution, seriousness, severity, cause, and action taken for any event on the AE eCRF.

Disease signs and symptoms that existed prior to the study injections are not considered AEs unless the condition recurs after the subject has recovered from the pre-existing condition or the condition worsens in intensity or frequency during the study.

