11.4.4 Adverse Events

Device-related AEs will be captured with TrackWise Enterprise Quality Management Software and coded using AE term codes. Treatment-emergent AEs will also be summarized by serious AEs (SAEs), AE severity, AE leading to treatment or study early termination, and relationship to study drugs/devices. SAEs will be coded using MedDRA version 17.0 or higher, and presented by system organ class and preferred term.

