18 CHANGES TO ANALYSES SPECIFIED IN PROTOCOL

Change to analyses specified in protocol is not applicable to this study.

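### SAP 11.1 tabulates adverse events leading to study discontinuation only, omits the stopping-of-treatment part of the summary in Protocol 11.4.4, and SAP 18 declares no change

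*SAP*

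**What the plan says.** Protocol 11.4.4 lists the ways in which treatment-emergent AEs will be broken down. After seriousness and severity it names "AE leading to treatment or study early termination, and relationship to study drugs/devices". Stopping treatment and leaving the study are both covered, whether they are read as one combined category or as two.

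SAP 11.1 sets out its tables under the sentence "AE summary tables will be presented for TEAEs only and will include the following". Six categories follow: all TEAEs, related TEAEs, "TEAEs leading to study discontinuation", serious/severe TEAEs, related serious/severe TEAEs, and TEAEs leading to death. The overall summary by treatment group is tied to these same categories. The section also states: "All TEAEs will be summarized by SOC, PT and treatment group using frequency counts and percentages". A further table adds maximum severity. On listings it says: "All AEs will be listed, and additional listings will be presented for AEs leading to discontinuation, serious AEs and AEs resulted in deaths".

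SAP 18 reads: "Change to analyses specified in protocol is not applicable to this study".

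On data capture, Protocol 10.2, which concerns device events, has the investigator record among other items "seriousness, severity, cause, and action taken for any event on the AE eCRF". Protocol 10.1, which concerns drug events, refers to the AE eCRF but does not name action taken.

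**The concern.** The protocol names an outcome that the SAP's summary list does not carry, and the SAP says that nothing was changed. A programmer who follows SAP 11.1 will produce a table of events that ended study participation and none of events that ended a treatment.

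In a single-product trial the two outcomes may nearly coincide. Here they can separate. BELKYRA subjects start at V1, and fillers, skin care and BOTOX Cosmetic begin at V7 for everyone. A subject may have BELKYRA stopped because of a reaction, move on to the later products and finish at V12. That subject is a study completer and does not enter the study-discontinuation table.

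What is at stake is how tolerability is reported. Protocol section 2 gives the lack of studies on the safety and impact of combined treatment as part of the rationale. A report showing few or no discontinuations for AEs could be read as saying that few or no subjects stopped a treatment for an AE, which the planned table would not establish.

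**Working it through.** The plan gives no figure to reproduce. The check is whether any planned output supplies what Protocol 11.4.4 promises for a subject who stops one treatment because of an AE and stays in the study.

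1. **Discontinuation table (SAP 11.1).** It is restricted to study discontinuation. The subject is not in it.
2. **All-TEAE tables by SOC and PT, and by maximum severity (SAP 11.1).** The event is counted. Nothing shows that treatment was stopped because of it.
3. **Related-TEAE table (SAP 11.1).** The event is counted if judged related. Again the action taken is not shown.
4. **Disposition (SAP 7).** It tabulates study completion as yes or no, and the reasons for leaving before V12. The subject is a completer. There is no row for stopping a product.
5. **Exposure and compliance (SAP 9).** These are descriptive statistics by product, by combination and overall, with no reason for stopping. The number of BELKYRA sessions is variable by design, up to 6: "The investigator will determine the number of treatment sessions based on his/her clinical experience" (Protocol Synopsis, dosing of BELKYRA). A low session count therefore does not distinguish a satisfactory result from a stop for an AE.
6. **Listings (SAP 11.1).** The event is in the listing of all AEs. It may also be in the listing of AEs leading to discontinuation, but the SAP does not say whether that word means the study, a treatment or both. On either reading this is a listing, not the summary in Protocol 11.4.4.
7. **Declared changes (SAP 18).** None.

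The event is thus counted in at least two tables and listed at least once. No summary table classifies it as leading to the stopping of a treatment.

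**Scale.** The documents give no rate of AE-driven stopping, so the understatement cannot be estimated. The planned sizes (Protocol 11.6: 60 subjects, about 20 of them on BELKYRA) show only what one case is worth:

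- in the BELKYRA group, 1/20 = 5.0 percentage points;
- overall, 1/60 = 1.7 percentage points.

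With k such subjects, all in the BELKYRA group, the SAP's table omits k × 5.0 points in that group and k × 1.7 points overall. The value of k is unknown and may be 0.

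**The case against.** The strongest reply is that little is lost. Every TEAE is tabulated by SOC and PT and by severity, and every AE is listed. The SAP also plans a listing of AEs leading to discontinuation whose wording, unlike that of the table, is not limited to the study. With 60 subjects a reader could go through that listing by hand. The phrase introducing the tables does not strictly make the list exhaustive. No objective in Protocol section 3 is a safety objective, safety is descriptive and untested, and no efficacy result depends on this.

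Most of that stands, and it limits the point. A reader might infer that a subject who stops one product for an AE disappears from the tables altogether. The documents do not support that: what is missing is one classification, not the subject or the event.

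A reader might also infer that stopping one product and carrying on is the usual outcome of an intolerable reaction. No section says so. Protocol 8.2 lists inability to tolerate the test treatment, and AEs that prevent continued participation, among circumstances that could end participation in the study; those subjects would be in the SAP's table. The visit-by-visit procedures in Protocol 6.2 are not visible in the copy available, so what follows an AE during the BELKYRA stage cannot be checked.

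The reply does not remove the mismatch. An ambiguous listing is not a summary, a list that may be added to at discretion is not prespecification, and SAP 18 still says that nothing changed. Protocol 11.7 expects changes to planned analyses to go through an amendment.

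**Conclusion.** The point holds as an undeclared gap between protocol and SAP in safety reporting. The SAP omits the stopping-of-treatment part of the summary in Protocol 11.4.4. No planned summary table identifies TEAEs that led to stopping a treatment in subjects who stayed in the study. The discontinuation table could understate AE-driven stopping of treatment, by an amount that the documents do not allow anyone to estimate.

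The conclusion on what is missing rests only on the visible text of Protocol 11.4.4 and SAP 7, 9, 11.1 and 18. The possible understatement needs one further assumption: that a subject can stop one product and remain in the study. The staged design makes this plausible, and Protocol section 5 refers to subjects who discontinue treatment. How often it would happen is not known, so a claim that tolerability will be materially overstated goes beyond the documents.

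It is worth correcting because the remedy is cheap and restores the protocol's own analysis. The primary and secondary efficacy conclusions are unaffected.

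**What to change.** - **SAP 11.1, tables.** Add the category *TEAEs leading to discontinuation of any study treatment*, whether or not the subject stayed in the study. Identify the product concerned and show the category separately from study discontinuation. State which products it covers: Protocol section 9 lists SkinMedica among the study treatments, whereas Protocol 10.1 says those products are not investigational and handles their AEs under separate procedures.
- **SAP 11.1, listings.** State that discontinuation in the listing covers both treatment and study, and show which applies.
- **AE eCRF.** Confirm that action taken is captured for drug AEs as well as device AEs. The protocol names it only for device events, while BELKYRA and BOTOX Cosmetic are drugs.
- **SAP 18.** If the summary cannot be produced, replace the statement of no change with a declaration of the omission and the reason for it.

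Full SOC and PT tables for each product and a new disposition row would go beyond what Protocol 11.4.4 promises and are not needed to close the gap. The change concerns reporting only and does not touch any rule on when a treatment is stopped.

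The cost is SAP wording, one extra summary row or table, and a check of one eCRF field, which could become a data-collection change if the field is missing for drug events. Reported tolerability may look slightly less favourable.

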4.1 Study Design Overview

This Phase 4 study is a prospective, interventional, multicenter, combination medical device, drug, and skin care postmarketing study. Each subject will be in the study for up to 11 months depending on the treatments given, and act as his/her own control. All products will be used as per their license only. The investigators will perform all treatments and evaluations.

[figure not shown]
The study is planned to enroll 60 subjects consecutively at approximately 6 study sites in Canada. The ratio of subjects treated with BELKYRA to subjects without BELKYRA treatment will be approximately 1:2 (ie, approximately 20 BELKYRA subjects and 40 subjects without BELKYRA) based on clinical indication and the decision of the subject and investigator. Thus approximately one-third of all subjects will receive BELKYRA treatment. Recruitment will also target men, who are typically under-represented in aesthetic studies.

Detailed descriptions of all study procedures by study visit and study treatment are presented in Table 6.1 and Section 6.

All subjects will sign an informed consent form (ICF) and begin at the screening visit (V0). Subjects receiving BELKYRA treatment will enter the study at V1 continuing on to V12. There will be at least 1 month between repeat BELKYRA treatments and the final BELKYRA treatment.

Subjects not receiving BELKYRA following screening (V0) will enter the study at V7 to begin treatment with Juvéderm HA facial fillers, SkinMedica, and BOTOX Cosmetic, as indicated in the study design diagram (Figure 4.1).

Figure 4.1 Overall Study Design

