11.1 General Statistical Considerations

A brief summary of the general statistical analysis methods is provided below; full details will be provided in a separate statistical analysis plan (SAP), which will be finalized prior to database lock.

Data will be summarized using descriptive statistics (number of observations [n], mean, standard deviation, median, minimum, and maximum for continuous variables; and n and percent for categorical variables).

Hypothesis testing will be performed at a 0.05 significance level (2-sided). In this study, BELKYRA and without BELKYRA is the major treatment difference between enrolled subjects. Hence, unless specified, all endpoints will be summarized by those two groups (BELKYRA and without BELKYRA) and overall respectively. However, this study is not designed to compare the efficacy and safety outcomes between subjects treated with BELKYRA and those treated without BELKYRA. All discussion and interpretation related to study outcomes will be mainly focused on the overall results.

Two critical time points, baseline and end of study, will be referenced in most of statistical analyses for this study. Baseline is defined as the latest assessment prior to any study treatments for each subject. End of study is the last clinical visit an enrolled subject has in this study. For BELKYRA subjects who complete this study, the final visit will be their V12 visit; for subjects who will not be treated with BELKYRA, this visit will also be the V12 visit after approximately 5 months of treatment. Subjects who discontinue will be asked to return for the last clinical visit for end-of-study data collection.

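### TEAE percentages take no account of follow-up that differs by design between the groups, so the two columns are not comparable and the overall figure mixes two lengths

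*SAP*

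**What the plan says.** **Follow-up.** Protocol 4.1 gives the two paths: "Subjects receiving BELKYRA treatment will enter the study at V1 continuing on to V12", and "Subjects not receiving BELKYRA following screening (V0) will enter the study at V7". On time in study, the same section says: "Each subject will be in the study for up to 11 months depending on the treatments given". Protocol 11.1 describes the final visit for the other group: "for subjects who will not be treated with BELKYRA, this visit will also be the V12 visit after approximately 5 months of treatment". The synopsis explains why the BELKYRA phase varies in length: "Up to 6 treatments spaced at intervals of no less than 1 month apart, are recommended". The planned split in Protocol 4.1 is "approximately 20 BELKYRA subjects and 40 subjects without BELKYRA".

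**Adverse event tables.** SAP 11.1 counts an event as treatment-emergent if it appears, worsens or becomes serious after treatment with the investigational products. On presentation it says: "All TEAEs will be summarized by SOC, PT and treatment group using frequency counts and percentages". A summary of the main TEAE categories is planned by group and overall. Event counts are also planned, without a time denominator. Exposure is summarized separately in SAP 9 and is not linked to adverse events.

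**Interpretation.** SAP 10, like Protocol 11.1, says the study was not set up to compare the two groups on efficacy or safety, and that discussion will centre on the overall results. SAP 11 specifies no safety test.

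**The concern.** Treatment-emergent time starts at about V1 in one group and V7 in the other. This inequality comes from the design, not from dropout. The percentage of subjects with at least one event generally rises with time at risk, so two groups with the same event rate can show different percentages.

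Two readings are affected. The first is the side-by-side one: the BELKYRA and without-BELKYRA columns describe different lengths of follow-up. The second is the overall percentage. It averages a longer and a shorter regimen, so it estimates the risk over neither, and its value depends on how many subjects of each kind are enrolled. The statement that the groups are not compared addresses the first reading only. Adverse events are the only safety parameter that SAP 11 names, so these tables carry the safety result.

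**Working it through.** The plan states no adverse event rate and no safety precision, so there is no figure of its own to reproduce. The calculation below shows the mechanism under stated assumptions. It is not a prediction.

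**Inputs from the documents**
- BELKYRA path V1 to V12, at most 11 months in study (Protocol 4.1)
- Other path V7 to V12, about 5 months of treatment (Protocol 11.1)
- Group sizes about 20 and 40 (Protocol 4.1)

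**Assumptions**
- The same constant event rate in both groups
- A 5-month risk p between 5% and 60%
- 11 months as the upper limit for BELKYRA, with 8 months as a shorter case for fewer sessions

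**Formulas**
- Risk over T months: q = 1 − (1 − p)^(T/5)
- Pooled percentage at 20:40: (20q + 40p)/60

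**Worked case, p = 20%, T = 11**
- q = 1 − 0.8^2.2 = 38.8%
- Pool = (20 × 38.8 + 40 × 20)/60 = 26.3%
- Underlying rate = −ln(0.8)/5 = 0.0446 per month, or 4.46 per 100 subject-months, identical in both groups

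| 5-month risk | 11-month risk | Ratio | Pool 20:40 | 8-month risk | Ratio |
|---|---|---|---|---|---|
| 5% | 10.7% | 2.1 | 6.9% | 7.9% | 1.6 |
| 10% | 20.7% | 2.1 | 13.6% | 15.5% | 1.6 |
| 20% | 38.8% | 1.9 | 26.3% | 30.0% | 1.5 |
| 40% | 67.5% | 1.7 | 49.2% | 55.8% | 1.4 |
| 60% | 86.7% | 1.4 | 68.9% | 76.9% | 1.3 |

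**Dependence on the mix** (p = 20%, T = 11)
- 10:50 gives (10 × 38.8 + 50 × 20)/60 = 23.1%
- 20:40 gives 26.3%
- 30:30 gives (30 × 38.8 + 30 × 20)/60 = 29.4%

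The event rate is the same in all three; only the enrolment differs.

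**Share of follow-up.** At most 20 × 11 = 220 subject-months for BELKYRA and 40 × 5 = 200 for the others. BELKYRA subjects are then 20/60 = 33% of subjects but up to 220/420 = 52% of follow-up.

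**Opposite extreme.** If every event were tied to the injections that both groups receive from V7 on, extra months would add nothing, and both columns and the pool would read 20%. With no BELKYRA-specific effect, the 20% case therefore spans 20% to 38.8% for the BELKYRA column and 20% to 26.3% for the pool. A real BELKYRA effect would come on top.

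**The case against.** A reader might infer that the BELKYRA column is inflated, or that it will show an excess from observation time alone. The documents do not support that. Each column is a correct crude incidence over the regimen that group receives. The extra months are BELKYRA treatment, not idle observation, so part of any excess may be a real product effect. This objection stands.

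The plan also limits the comparison itself. It disclaims a safety contrast between the groups and tests nothing. The groups are formed by clinical indication and choice, with eligibility criteria specific to BELKYRA, so equal follow-up would not make them comparable. This also stands, but it leaves the overall percentage untouched. The split is only approximately 1:2. The synopsis lets the sponsor close recruitment to one group, which should hold the mix near target, but the target is itself a design choice.

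The illustration has real weaknesses. Eleven months is a maximum time in study, apparently counted from screening, whereas 5 months is time on treatment. The synopsis gives about 11 months per subject, depending on treatments, which fits loosely with 5 months for the larger group. The visit schedule is not visible to settle it. A constant rate is a rough model for injectables: Protocol 10.3 has subjects keep a reaction diary for 30 days after each filler treatment, and events may cluster there. Rows for single preferred terms may be rare. At 0.005 per month, 1 − exp(−0.025) = 2.5% against 1 − exp(−0.055) = 5.4%, a gap of under 3 points, when one BELKYRA subject is 1/20 = 5 points.

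Finally, the listings, event counts, exposure tables and separate group columns let a careful reader see the mix. They do not give a percentage over a common window.

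**Conclusion.** The point holds in limited form. SAP 11.1 reports crude TEAE percentages over follow-up that differs by design. The group columns are each valid but not comparable, and the overall percentage, where interpretation is directed, combines two lengths and varies with the enrolment mix.

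The size is unknown. Under an equal constant rate and 5-month risks of 5% to 60%, follow-up alone would raise the 11-month percentage 2.1-fold down to 1.4-fold over the 5-month one, or 1.6-fold down to 1.3-fold at 8 months. These ratios rest on assumed rates and on 11 months as a maximum. They are near the upper end if events cluster around the shared injections, and they say nothing about whether BELKYRA causes more events.

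Because safety is descriptive and untested, no hypothesis test is affected. This is a worthwhile, cheap improvement to the SAP, not a flaw that threatens the study.

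**What to change.** Add to SAP 11.1:

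1. **TEAE tables by period of onset.** Period 1 runs from first BELKYRA treatment to before V7, for BELKYRA subjects only. Period 2 runs from V7 to V12, for both groups and overall. Assign each event by its onset date. SAP 16.2.1 does not impute incomplete dates, so state where events without a usable onset date are shown, for example in a separate row.
2. **As a supplement, events per 100 subject-months**, by group and overall. Add a note that injection-related events cluster around treatments, so a constant rate is only approximate.
3. **A footnote to the existing percentages** giving the follow-up time in each group.

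The period table matters more than the rate. It separates BELKYRA-phase events and gives both groups a common window, which a rate cannot do. It does not turn V7 to V12 into a clean comparison, since late BELKYRA effects may still start there and the groups are self-selected.

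The cost is SAP wording and one or two more descriptive tables. Event onset (Protocol 10.2) and product exposure (Protocol 11.3) are already recorded. The period 1 table will rest on about 20 subjects and will be imprecise. Conduct, sample size and testing do not change.

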10.7.2 Relationship to Study Product

A determination will be made, by the investigator, of the relationship, if any, between an AE and any study product, anesthesia employed, the study device, or the injection procedure, as applicable, using the guidelines presented in Table 10.2.

Table 10.2 Guidelines for Determining the Relationship Between Adverse Event and the Study Product

Highly Probable	This causal relationship is assigned if the AE starts a reasonable time after the administration of study product, stops/improves when the study product is stopped, and could reasonably be explained by known characteristics of the study product.
Probable	This causal relationship is assigned when the AE starts a reasonable time after the administration of study product, stops/improves when the study product is stopped, and could not be reasonably explained by known characteristics of the subject’s clinical state.
Possible	This causal relationship is assigned when the AE starts a reasonable time after the administration of study product, but could be produced by the subject’s clinical state or other modes of therapy administered to the subject.
Not Related	This causal relationship is assigned when the time association or the subject’s clinical state is such that the study product was not likely to have had an association with the observed AE.

Abbreviations: AE = adverse event.

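### The SAP's definition of a related adverse event does not use the protocol's causality scale: the top grade, Highly Probable, is unmapped, and the related summaries name drugs but not devices

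*SAP*

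**What the plan says.** Protocol 10.7.2 asks the investigator to judge the relationship "between an AE and any study product, anesthesia employed, the study device, or the injection procedure", using Table 10.2. That table has four grades: "Highly Probable", Probable, Possible and Not Related.

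SAP 11.1 turns the grades into a yes/no classification: "An AE will be considered as related if the event is Possibly, Probably or Definitely related". It adds a rule for blanks: "If the relationship to study drug is missing, the AE will be treated as related".

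The classification feeds two of the six TEAE summary categories listed in SAP 11.1: "TEAEs related to study drug" and "Serious/Severe TEAEs related to study drugs". A separate counting rule, for incidence by system organ class, preferred term and "relationship to investigational product", says that for repeated events "only the most related occurrence will be included in the incidence". That rule needs the grades to be ordered.

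Protocol 11.4.4 plans a summary of TEAEs by relationship to study drugs/devices. SAP 18 says there are no changes to the analyses specified in the protocol.

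**The concern.** The sentence that decides which events count as related is an operative programming rule, and its labels are not the labels that investigators are told to use. A programmer who codes it as written would search for a value that Table 10.2 does not offer and would ignore the strongest value that it does offer. A blank would count as related and a Highly Probable would not. That reverses the cautious intent shown by the rule for blanks.

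The drug-only wording is a second, smaller mismatch on the same outputs. Protocol 4.1 describes a combined device, drug and skin care study, so a summary limited to drugs would be narrower than the one protocol 11.4.4 plans.

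At stake is whether the related and serious/severe-related counts can be reproduced. Two programmers could get different figures from the same data. Safety is descriptive and untested (SAP 11), so no inferential result depends on this.

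**Working it through.** The plan gives no figure to reproduce here. The check is a comparison of two sets of labels and of the wording around them.

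**Step 1: grades.** The scale comes from protocol Table 10.2 and the rule from SAP 11.1.

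| Recorded value | On the protocol scale? | SAP 11.1 read literally | SAP 11.1 if Definitely means Highly Probable |
|---|---|---|---|
| Highly Probable | yes | not counted as related | related |
| Probable | yes | related | related |
| Possible | yes | related | related |
| Not Related | yes | not related | not related |
| Missing | (blank) | related | related |
| Definitely | no | related, but no such grade to record | (same as first row) |

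The protocol has 3 grades above Not Related, and the SAP list has 3 terms. Matched: 2 (Possible, Probable). On the scale but unmapped: 3 − 2 = 1 (Highly Probable). In the SAP but not on the scale: 3 − 2 = 1 (Definitely).

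The missing-relationship rule does not rescue the unmapped grade, because Highly Probable is a recorded value.

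**Step 2: outputs affected.** Of the 6 listed TEAE summary categories, 2 depend on the related classification. The incidence by relationship also uses the scale: choosing the most related occurrence requires a place for Highly Probable in the order, and the SAP gives none.

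**Step 3: outputs not affected.** The all-TEAE summary, the tables by system organ class and preferred term, the table by maximum severity and the listing of all AEs do not use the related classification. A Highly Probable event appears in each of these as it would otherwise.

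**Step 4: the object of the relationship.** Both related summaries and the missing-relationship rule refer to study drug or study drugs, so the drug-only wording occurs in 3 places. Protocol 11.4.4 says drugs/devices. SAP 18 declares no departure, so a drug-only summary is not a stated choice. SAP 11.1 itself uses a third term, investigational product, for the incidence by relationship.

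**Step 5: size of the effect.** If Definitely is read as Highly Probable, the shortfall from the grade mismatch is 0. If it is coded literally, the shortfall is the number of subjects whose only related TEAEs are graded Highly Probable. The documents give no adverse event rates, so that number cannot be computed.

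**The case against.** The best answer on the grades is that this is a label slip with one sensible reading. Both documents have three ordered terms above Not Related, and a SAP that counts blanks as related did not mean to discard the strongest grade. The eCRF is also not among the documents, so the label actually recorded could differ from Table 10.2. This largely stands: the mislabel is the likely explanation. It does not remove the need to correct the text. Table 10.2 is the only scale shown, and if the eCRF does say Definitely, the protocol and the eCRF disagree and need aligning.

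On devices, the protocol synopsis lists six investigational products, four of them the Juvéderm fillers. SAP 11.1 defines TEAEs by treatment with investigational products and sets a counting rule by relationship to investigational product. Study drug is therefore probably loose shorthand, and a SAP that declares no change should be read alongside protocol 11.4.4. This also stands in good part, but the two listed summaries and the missing-relationship rule still carry the narrower term.

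A reader might infer that device events will be missing from the safety tables because protocol 11.4.4 captures device-related AEs in a separate software system. The documents do not support that. Protocol 10.2 records device AEs on the AE eCRF, and SAP 11.1 classifies all AEs.

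A reader might also want anesthesia and the injection procedure added to the related summaries, since protocol 10.7.2 names them. Protocol 11.4.4 asks only for drugs/devices, so that would go beyond the planned summary.

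**Conclusion.** The SAP rule is wrong as written but minor. One of three related grades is unmapped, and one SAP term is not on the protocol's scale. Two listed summaries and the ordering rule for a third output are affected. The drug-only wording in three places departs from protocol 11.4.4 without being declared, though loose terminology is the likely cause.

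The conclusion assumes that Table 10.2 is the scale recorded on the eCRF. The consequence ranges from zero, if the programmer reads Definitely as Highly Probable, to an undercount of the related and serious/severe-related TEAEs that cannot be sized from the documents.

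It would be tempting to conclude that the most clearly treatment-caused events will disappear from the safety report. They will not: they remain in the all-TEAE and severity tables and in the listings.

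Two neighbouring questions are not part of this finding. One is whether injection site reactions kept only in the 30-day diary count as TEAEs. That may be settled in the visit procedures, Table 6.1 or the redacted SAP text, none of which is visible. The other is the handling of events related to SkinMedica products, which protocol 10.1 says are not investigational products and assigns to separate procedures.

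**What to change.** Change SAP 11.1 as follows:

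1. Define a related AE as one graded Possible, Probable or Highly Probable on protocol Table 10.2, or one with a missing relationship. Delete Definitely.
2. For the most-related-occurrence rule, state the order, with Highly Probable highest, then Probable, Possible and Not Related.
3. Replace study drug or study drugs with study drugs/devices in both related-TEAE summaries and in the missing-relationship rule, to match protocol 11.4.4.

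Before programming, confirm that the eCRF labels are those of Table 10.2.

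The cost is a few lines of SAP wording, with no new data. The downside is that reported related-event rates may be slightly higher than under a literal reading of the present text.
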